2.2. Study Objective(s) and Endpoint(s)

Objectives	Endpoints	
Primary Objectives	Primary Endpoints	
Evaluate long-term safety and tolerability of belimumab in subjects with SLE in Japan and Korea	The endpoints below will be used to assess this study objective.	
	Adverse events (AEs)	
	 Frequency and percentage of subjects with events. Event rates adjusting for person-years on study agent. Laboratory Parameters Observed and Change from Baseline by visit. Laboratory reference shifts from baseline by visit. Laboratory toxicity worsening of at least two grades from baseline by study year Grade 3 or 4 laboratory abnormalities by visit and study year. 	
	Immunogenicity	
	Immunogenic response (anti-belimumab anti-bodies) by visit and study year.	
	Biomarkers	

[figure not shown]
Objectives	Endpoints
Coonday Objectives	 Percent change from baseline in immunoglobulins, auto-antibodies, and complement levels by visit. Immunoglobulin values below the lower limit of normal by visit and study year. Percent change from baseline in absolute B cell subsets.
Secondary Objectives	SRI and Other Secondary Endpoints
Evaluate the long-term efficacy of belimumab in subjects with SLE in Japan and Korea	SRI response rate at each scheduled visit when complete efficacy evaluations occur (e.g., Week 24 and Week 48 for each year). An SRI response is defined as
	 ≥4 point reduction from baseline in SELENA SLEDAI score, AND
	No worsening (increase of <0.30 points from baseline) in Physician's Global Assessment (PGA), AND
	 No new BILAG A organ domain score or 2 new BILAG B organ domain scores compared with baseline at the time of assessment.
	 Percent of subjects with ≥4 point reduction from baseline in SELENA SLEDAI score assessed every 24 weeks Percent of subjects with No Worsening in PGA compared
	to baseline (added to the RAP)
	Percent of subjects with No new BILAG A organ domain or 2 new BILAG B organ domain scores compared to baseline (added to the RAP)
	 Number of days of daily prednisone dose ≤ 7.5 mg/day
	and/or reduced by 50% from baseline over time.
	Time to first severe SLE Flare Index (SFI) flare assessed over time.
	Other Efficacy Endpoints
	Disease Activity
	Absolute change and percent change from baseline in SELENA SLEDAI (added to the RAP)
	Change in Systemic Lupus International Collaborating Clinics (SLICC)/ACR Damage Index assessed every 24 weeks.
	SLICC/ACR Damage Index Worsening from baseline (added to the RAP).
	Percent change from baseline in PGA assessed every 24 weeks.
	Flares
	Time to first SFI flare assessed over time.
	Time to first 1A/2B BILAG flare assessed over time.
	Time to first BILAG A flare assessment over time.
	Organ-specific measures
	Renal flare rate and time to first renal flare assessed over

The GlaxoSmithKline group of companies

BEL114333

Objectives	Endpoints
	time.
	Percent change from baseline in proteinuria by visit.
	Prednisone
	Percent change from baseline of prednisone dose at each scheduled visit.
	 Percent of subjects whose average prednisone dose has been reduced to ≤ 7.5 mg/day from >7.5 mg/day at baseline over time.

2.3. Study Design

Overview of S	Study Design and Key Features
	 The first dose in BEL114333 must be given 4 weeks (minimum of 2 weeks, maximum of 8 weeks) after the last IV dose for subjects enrolled from the parent study BEL113750. For subjects from the SC parent study BEL112341, the first IV dose in BEL114333 is targeted for 1 week after the last dose of SC belimumab (scheduled for Week 23 in the OL extension part of BEL112341). If a subject misses 3 or more consecutive infusions during BEL114333, they should be withdrawn from the study.
Time & Events	Refer to Appendix 1: Time & Events
Treatment Assignment	Open-label – all subjects will receive IV belimumab
Interim Analysis	• None

2.4. Statistical Hypotheses

Since this is an open-label continuation, no formal statistical hypothesis testing will be performed. Any comparisons between the parent study randomised treatment groups will be purely descriptive.

2.4.1. Treatment Comparisons

All subjects will be treated with open-label IV belimumab for the duration of the study BEL114333. The analyses will be performed on data from all subjects as one total belimumab treatment group by year of belimumab treatment.

As subjects started to receive belimumab treatment in the parent study, or the open-label extension of the parent study BEL112341, or the open-label study BEL114333, different time points to start of belimumab treatment will be used to define subject follow up in the analysis. See Figure 1.

Analyses will be based on all available follow-up from the first dose of belimumab treatment through to study end.

Additional safety (e.g., labs), efficacy and study population summaries will be presented by parent study randomised treatment groups (belimumab vs placebo); however, these comparisons will be descriptive in nature. For the remainder of the document, parent randomised treatment group will be used to refer to the treatment to which a subject was randomised in the parent study, irrespective of formulation.

Figure 1 First Belimumab Dose/Baseline Definition

Analyses will be based on all available data from the first belimumab dose through to study end, BEL114333. As subjects started to receive belimumab in the parent study, or the open-label extension of BEL112341, or the open-label study BEL114333, different timepoints to start of belimumab treatment are used in the analysis (as shown). Baseline is defined as the last available value prior to the first belimumab dose.

3. PLANNED ANALYSES

3.1. Interim Analyses

To date, no interim analyses pertaining to open-label safety data has been required to support regulatory submission activities for Japan, Korea and China.

3.1.1. Safety Reviews

The SRT regularly performs in stream data looks of the pooled open-label data from BEL114333, Japan and Korea subjects, and BEL113750, China subjects, to monitor the safety of these studies. These reviews are based on data from all subjects as one belimumab treatment group.

Additionally, the SRT performs in stream adjudication of subject-level data for Adverse Events of Special Interest (AESIs; serious and non-serious). See Appendix 10: PSAP Sections for AESI Reporting..

3.2. Final Analyses

Korean sites in BEL114333 were closed in 2015 (per the protocol-defined stopping criteria) because of approval and the commercial availability of Benlysta in Korea. The last subject visit in Korea was 27 April 2015.

The data base can be locked since all Japan and Korea subjects have completed their last visits of BEL114333. All Japanese subjects completed their latest visit, as appropriate, up to 6-month post-treatment follow-up visit. The 6-month FU serves as the last subject last visit. The last subject visit in Japan was on 13 September 2018.

The final planned primary analyses will be performed after the completion of the following sequential steps:

- 1. All subjects have completed the study as defined in the protocol.
- 2. All required database cleaning activities have been completed and final database release and database freeze has been declared by Data Management.

4. ANALYSIS POPULATIONS

All Subjects	 Japan and Korea subjects who were randomised in the DB 52-week parent study BEL113750. Additionally, participation in BEL114333 was extended to Japanese subjects in the parent study BEL112341, of which 30 subjects were randomised at the beginning of BEL112341 (but only 27 remained to enter the openportion of BEL112341). A total of 25 of these 27 subjects elected to join BEL114333; the other 2 did not elect to join BEL114333. This population, and all subsequently defined 	Enrolment and Population level displays for patient disposition
	This population, and all subsequently defined	

	populations below, will be based on data from all subjects as one total belimumab treatment group. Additional summaries will be presented by the parent randomised treatment groups. See Section 2.4.1.	
Screened	All subjects in the All Subjects population who completed the parent studies BEL113750 (Japan and Korea) or BEL112341 (Japan only) and were eligible to enrol in BEL114333.	Study Population
Enrolled	All subjects who enrolled in BEL114333.	Disposition-level displays
Safety	All subjects in the Enrolled population who received at least one IV dose of belimumab during BEL114333. Analyses will be based on all available follow-up from the first dose of belimumab treatment through to study end. See Section 2.4. As such exposure data to belimumab will be included for subjects who received their first dose in the parent study, and subsequently enrolled in BEL114333.	Safety/Efficacy analyses and displays
	Note: although the OL analysis for Japan and Korea will be based on the Safety population, the definition is the same as the Efficacy population used for China (which excluded subjects from one site).	

Refer to Appendix 12: List of Data Displays which details the population used for each display.

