4.2. Inclusion Criteria

Specific information regarding warnings, precautions, contraindications, adverse events, and other pertinent information on belimumab that may impact subject eligibility is provided in the Investigator Brochure (IB).

Deviations from inclusion criteria are not allowed because they can potentially jeopardize the scientific integrity of the study, regulatory acceptability or subject safety. Therefore, adherence to the criteria as specified in the protocol is essential.

Subjects eligible for enrolment in the study must meet all of the following criteria:

1. Have completed the BEL113750 Protocol in Northeast Asia through Week 48 OR have completed the open-label extension of C1115 in Japan.
2. Be able to receive the first dose of belimumab for BEL114333 four weeks (minimum of 2 weeks, maximum of 8 weeks) after the last dose in BEL113750 OR be able to receive the first dose of IV belimumab 1 week (plus a 1 week visit window) after the last dose of open-label SC belimumab in C1115.

3. A female subject not pregnant or nursing is eligible to enter the study if at least one of the following conditions apply:
- Of non-childbearing potential (i.e., women who had a hysterectomy, are postmenopausal which is defined as 1 year without menses, have both ovaries surgically removed or have current documented female sterilization procedure); or
 - Of childbearing potential (i.e., women with functional ovaries and no documented impairment of oviductal or uterine function that would cause sterility). This category includes women with oligomenorrhoea (even severe), women who are perimenopausal or have just begun to menstruate. These women must have a negative urine pregnancy test at screening, and agree to one of the following:
 - Complete abstinence from penile-vaginal intercourse, when this is the female's preferred and usual lifestyle, from 2 weeks prior to administration of the first dose of belimumab until 16 weeks after the last dose of belimumab; or
 - Consistent and correct use of one of the following acceptable methods of birth control for 1 month prior to the start of belimumab and for 16 weeks after the last dose of belimumab:
 - Implants of etonogestrel or levonorgestrel;
 - Estrogenic vaginal ring
 - Injectable progesterone;
 - Any intrauterine device (IUD) or intrauterine system (IUS) with a documented failure rate of less than 1% per year;
 - Oral contraceptives (either combined or progesterone only);

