- [8] Kaplan-Meier plot of time (in days) to withdrawal (see footnote 6 for definition of withdrawal) and associated summary table. See Section 11.5.1 for derivation of time to withdrawal. Note: subjects who died or completed the study per the protocol, will be censored.
- [9] Summarises No. (%) of subjects starting each year interval, and of those, the number completed, died and withdrawn [and reason for withdrawal], or ongoing in the study at the end of that year interval. Will be summarised using frequencies and percent. The denominator for each year will be the number of subjects who started each year of treatment.

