11.2.1. Year Intervals

- To report subject disposition and AE assessments with similar durations of exposure to active belimumab treatment, assessments will be slotted into year intervals using a 365-day calendar year.
- Few subjects are expected to have > 6 years exposure and therefore "Year 6+" will be extended to the last available visit.
- For subjects who withdraw during an interval, the end date of their final interval will be set to their exit visit date.
- For summaries, the "Any Time Post-Baseline" includes the follow-up visits, where follow-up visits are excluded from the "Year 6+" year interval.
- For laboratory assessments, the worst value/highest toxicity reported over the year
 interval will be used in the analyses. Concomitant medications will be reported by
 what medications a subject is taking during the interval. In addition, AEs will be
 reported by start date. Subject disposition, worst value/highest toxicity laboratory
 assessments, concomitant medications, and AEs will be summarized according to the
 following year categories.

Study Year	Belimumal	o Study Days
	Start Day	End Day
Year 0-1	Day 1 ^[1] First Treatment Date	Day 365
Year 1-2	Day 366	Day 730
Year 2-3	Day 731	Day 1095
Year 3-4	Day 1096	Day 1460
Year 4-5	Day 1461	Day 1825
Year 5-6	Day 1826	Day 2190
Year 6+	Day 2191	Maximum Study Day [2]

NOTES:

- [1] Protocols specify Day 0 as First Treatment, but due to CDISC standard implementation first treatment date will appear as Day 1 in the analyses. Also, first treatment date refers to first belimumab treatment, regardless of originally randomized treatment.
- [2] Last visit date will be defined as the exit visit date where applicable. Subjects who do not have an exit visit date and only a follow up date, the date of the follow up will be used. See Section 11.5.1 for more details.

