11.5. Appendix 5: Derived and Transformed Data

11.5.1. **General**

Subject Identifier, Breaks in Treatment and Date of Last Visit

Subject Identifier

- Subjects enrolled in BEL114333 from the parent study BEL113750 continued to use the same subject identifier as assigned in the parent study. Note: the site identifiers used in the parent study BEL113750 were changed in BEL114333 in order to retain the same subject identifier.
- Subjects enrolled in BEL114333 from the parent study BEL112341 were assigned subject identifiers ranging from 9001 to 9030.

Dose Interruption

- The first dose in the study BEL114333 must be given 4 weeks (minimum of 2 weeks, maximum of 8 weeks) after the last IV dose for subjects enrolled from the parent study BEL113750.
- For subjects from the SC parent study BEL112341, the first IV dose in study BEL114333 is targeted for 1 week (+1 week window) after the last dose of SC belimumab (scheduled for Week 23 in the OL extension part of BEL112341).

Note: For the purposes of reporting, dose interruptions will be ignored and exposure will be treated as continuous.

Date of Last Visit

- Last visit date (in BEL114333) will be defined as the exit visit date, where available.
- For subjects who do not have an open-label exit visit date, and only have a follow up date, the following will be used to derive a last visit date in order of priority:
 - 1. Death Date if non-missing and prior to Disposition Date
 - 2. Disposition Date, if non-missing
 - 3. If last non-follow up visit is after last dose of belimumab, use the minimum of a) the last non-follow up visit date, or b) the last dose date + 28 days.
 - 4. If the last non-follow up visit is prior to the date of last dose, use the last dose date.
- Time to withdrawal (in days) will be calculated for each subject as
 - O Time to Withdrawal = Date of Last Visit First Dose Date of Belimumab + 1

Date of Last Contact

 Final contact (in BEL114333) will be defined as the latest visit, as appropriate, up to the 6 month FU visit (post-last dose of belimumab).

Multiple Measurements at One Time Point

 Subjects having both High and Low values for Normal Ranges at any post-baseline visits for safety parameters will be counted in both the High and Low categories of "Any visit postbaseline" row of related summary tables. This will also be applicable to relevant Potential Clinical Importance summary tables.

Study Day

- Calculated as the number of days from first dose date of belimumab treatment:

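### Time to withdrawal and yearly withdrawal and death count belimumab time before BEL114333 Day 0 as time at risk, although every analysed subject had to complete a parent study to be included

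*SAP*

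**What the plan says.** **Who is analysed.** Entry to BEL114333 requires the subject to "Have completed the BEL113750 Protocol in Northeast Asia through Week 48 OR have completed the open-label extension of C1115 in Japan" (Protocol 4.2). The Safety population is then "All subjects in the Enrolled population who received at least one IV dose of belimumab during BEL114333" (SAP section 4). For the SC parent study the SAP gives the flow: 30 Japanese subjects randomised, 27 reaching the open-label part, and "A total of 25 of these 27 subjects elected to join BEL114333".

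**When the clock starts.** The general rule is "Analyses will be based on all available follow-up from the first dose of belimumab treatment through to study end". Time to withdrawal is the date of last visit minus "First Dose Date of Belimumab + 1", and the last visit is defined within BEL114333 (SAP 11.5.1). Year 0-1 covers Days 1 to 365 counted from the first belimumab dose, in whichever study that was given. The stated aim is: "To report subject disposition and AE assessments with similar durations of exposure to active belimumab treatment, assessments will be slotted into year intervals" (SAP 11.2.1).

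**How the displays are built.** For the Kaplan-Meier display, SAP 6.1 (Table 3, note 8) specifies only censoring: "Note: subjects who died or completed the study per the protocol, will be censored". For completion status by year (note 9), which includes died and withdrawn, "The denominator for each year will be the number of subjects who started each year of treatment". Tables 1.6 and 1.7 and Figure 2.1 all use the Safety population (SAP Appendix 12). Neither document mentions delayed entry or left truncation.

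**The concern.** A subject who left or died during parent-study belimumab treatment is not in the Safety population. The subjects who are in it carry their parent-study belimumab time into the risk set. That time is free of withdrawal and death because of how the population was selected, yet it is treated as if either could have happened in it.

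Two things follow. Early withdrawal and death are displayed too low. And because the protected time lies almost wholly in Year 0-1, with some in Year 1-2, a constant risk is displayed as increasing with years on drug. These are descriptive disposition displays and not listed endpoints, but they bear on long-term tolerability, which is part of the primary objective (Protocol 2.1).

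**Working it through.** The plan has no sample size, power or projected withdrawal figure, so there is nothing of its own to reproduce. The check is of the protected time and its effect.

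**1. Days from first belimumab to BEL114333 Day 0.** Inputs: the visit mapping in SAP 11.2.2 and note 1 to Protocol Table 2.

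| Parent arm | Offset (days) | Share of Year 0-1 | Share of Year 1-2 |
|---|---|---|---|
| IV belimumab | 364 | 364/365 = 99.7% | 0 |
| SC belimumab | 364 + 168 = 532 | 100% | (532 − 365)/365 = 45.8% |
| SC placebo | 168 | 168/365 = 46.0% | 0 |
| IV placebo | 0 | 0 | 0 |

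The first dose is Day 1, so the entry study day is the offset plus 1. Under the rule of 2 to 8 weeks after the last parent dose (Week 48, day 336), the IV belimumab offset runs from 336 + 14 = 350 to 336 + 56 = 392.

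**2. Effect on the displays.** Every withdrawal time is at least as long as the subject's offset, because the last visit is taken in BEL114333. With no delayed entry, a Kaplan-Meier estimate has all subjects at risk from Day 1. Table 1.6 likewise has all of them in its Year 0-1 denominator.

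**3. Illustrative size.** The documents do not give the number from BEL113750, the arm split or the withdrawal count. Assumed: a constant hazard equal in all groups; no administrative censoring in the years shown; a belimumab share f of 0.50 to 0.67 in both parent studies; an SC share s of 0.10 to 0.40 (not zero, since 25 SC subjects joined). With a true yearly risk w:

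- h = −ln(1 − w)/365 and r(e) = 1 − exp(−h·max(0, t − e))
- Displayed risk at day t = (1 − s)[f·r(364) + (1 − f)·r(0)] + s[f·r(532) + (1 − f)·r(168)]

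At w = 10% and t = 365: r(0) = 10%, r(168) = 5.53%, r(364) = 0.03%, r(532) = 0.

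- Lowest (f = 0.67, s = 0.4): 0.6(0.67 × 0.03% + 0.33 × 10%) + 0.4(0.33 × 5.53%) = 2.7%
- Highest (f = 0.5, s = 0.1): 0.9(0.5 × 0.03% + 0.5 × 10%) + 0.1(0.5 × 5.53%) = 4.8%

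| True yearly risk | Displayed at 1 year | Displayed at 2 years | True at 2 years |
|---|---|---|---|
| 5% | 1.4-2.4% | 5.7-7.2% | 9.8% |
| 10% | 2.7-4.8% | 11.3-14.1% | 19.0% |
| 15% | 4.1-7.2% | 16.7-20.8% | 27.8% |

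Among subjects starting each year, a constant 10% would read 2.7-4.8% in Year 0-1, 8.8-9.8% in Year 1-2 and 10% in Year 2-3.

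**4. Does delayed entry repair the curve?** A simulation used a hazard of 0.10 per year and an assumed mix of 50% IV belimumab, 30% IV placebo, 13% SC belimumab and 7% SC placebo. The planned method gave 96.8% withdrawal-free at 1 year. Delayed entry gave 90.5%, matching the true 90.5%.

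**5. Does moving the denominator repair Table 1.6?** No. An IV belimumab subject nominally enters on Day 365 and so still counts as a Year 0-1 subject for one day. Only SC belimumab subjects drop out, and the Year 0-1 percentage becomes {(1 − s)[f·r(364) + (1 − f)·r(0)] + s(1 − f)·r(168)}/(1 − s·f). At w = 10% this is 3.4% (f = 0.67, s = 0.1) to 5.1% (f = 0.5, s = 0.4), still well below 10%. A rate over person-years at risk from Day 0 does not depend on that one day: under the same assumptions it is 100 × (−ln 0.9) = 10.5 per 100 person-years in every interval.

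**The case against.** The time origin is disclosed (SAP 2.4.1 and 5.1) and was chosen for consistency with the other long-term continuation studies. Table 1.1 sets parent-study randomisation and completion beside enrolment, Table 1.3 gives person-years by interval and parent arm, and Listing 2 gives time of withdrawal. If Tables 1.6 and 1.7 are split by parent arm, the flat first year of the belimumab arm would be visible. The mock shells are a separate document, so planned footnotes and numbers at risk cannot be judged. All analyses are descriptive. All of this stands, and it limits the weight of the point. None of it changes the curve or the yearly percentages: it lets a careful reader see the problem without correcting it.

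A reader might infer more than the documents support:

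- **That ordinary AE, SAE and laboratory summaries are biased in the same way.** They are not: such events during parent-study belimumab time are counted.
- **That the yearly death columns of Tables 2.6, 2.39 and 2.47 are event-free before Day 0.** AE tables are slotted by AE start date (SAP 7.2.1, 11.3.2), so a fatal event that began in the parent study could fall in an earlier year. How the death rows are dated depends on the unseen shells.
- **That a death rate is diluted in Table 2.48.** No stand-alone death-rate table is listed, and whether that table has a death row is unknown.
- **That 5 of 30 SC subjects (16.7%) is an early withdrawal rate on belimumab.** The arm is not stated, and two of the five chose not to join.

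**Conclusion.** The point holds for Table 1.7, Figure 2.1 and the withdrawn and died entries of Table 1.6. The protected time follows from the documents alone: nominally 364, 532, 168 and 0 days for IV belimumab, SC belimumab, SC placebo and IV placebo. So does the direction: early withdrawal and death too low, with an apparent rise over the years under constant risk.

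The size cannot be computed from the documents. The figure of about 3-5% shown for a true 10% in Year 0-1 rests on the assumed hazard, arm shares and SC share, and is an illustration only.

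This is a bias in descriptive estimates, not an error-rate problem. Any-time death percentages and completion counts, which are administrative, are outside it.

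**What to change.** Keep the belimumab-time axis.

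- **Figure 2.1 and Table 1.7:** use Kaplan-Meier with delayed entry at BEL114333 Day 0, and show numbers at risk.
- **Table 1.6:** keep the planned counts. In place of the percentage of subjects starting the year, report withdrawals and deaths per 100 person-years at risk from BEL114333 Day 0 in each interval.
- **Tables 2.6, 2.39 and 2.47:** leave as planned, with a footnote to the yearly death columns that all analysed subjects had to survive to BEL114333 Day 0.

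The cost is SAP wording, one entry-date variable that is already held, and a footnote. Estimates before Day 169 would nominally rest on IV placebo subjects alone, whose number the documents do not give, and would be less precise and less favourable. The yearly disposition figures would no longer compare directly with the other long-term continuation studies unless the planned version is kept as a supplementary display.
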